7 STUDY INTERVENTION(S) AND CONCOMITANT THERAPY

Study intervention is defined as any investigational intervention(s), marketed product(s), placebo, procedure(s), or medical device intended to be administered to a study participant according to the study protocol.

Study intervention includes investigational (medicinal) product (IP/IMP) as indicated in [Table 7.1-1](#).

An IP, also known as IMP in some regions, is defined as a pharmaceutical form of an active substance or placebo being tested or used as a reference in a clinical study, including products that already have a marketing authorization but are used or assembled (formulated or packaged) differently from the authorized form, used for an unauthorized indication, or used to gain further information about the authorized form.

7.1 Study Interventions Administered

Details of the IP used for both cohorts are provided in Table 7.1-1:

Table 7.1-1: Study Interventions

	Study Intervention Details (for Cohort 1 and Cohort 2)
Intervention Name	Ozanimod (Zeposia)
Type	Drug
Dose Formulation	Capsule
Unit Dose Strength(s)	0.23 mg, 0.46 mg, and 0.92 mg
Dosage Level(s)	Days 1–4: 1 × 0.23 mg (QD) Days 5–7: 1 × 0.46 mg (QD) Day 8 and thereafter : 1 × 0.92 mg (QD)
Route of Administration	Oral
Use	Active
Sourcing	Provided by the Sponsor
Packaging and Labeling	Ozanimod will be packaged and labelled per country requirements.
Current/Former Name(s) or Alias(es)	RPC1063, BMS-986374

Table 7.1-2Participants will receive a phone call on Day 5 (when titrating their dose from 0.23 mg to 0.46 mg) and again on Day 8 (when titrating their dose from 0.46 mg to 0.92 mg) as a reminder about the dose adjustment (see [Table 2-1](#)).

Table 7.1-2: Ozanimod Dose Titration Regimen

Days	Regimen
Days 1–4	0.23 mg QD PO
Days 5–7	0.46 mg QD PO
Day 8 and thereafter	0.92 mg QD PO

7.2 Method of Study Intervention Assignment

Study using interactive response technology (IRT): All participants will be centrally assigned using IRT. Before the study is initiated, each user will receive log-in information and directions on how to access the IRT.

The study intervention will be dispensed at the study visits as listed in the SOA ([Section 2](#)).

During the screening visit, the investigative site will access the screening option of the IRT designated by BMS for the assignment of a 5-digit participant number that will be unique across all sites. Enrolled participants, including those who are not dosed, will be assigned sequential participant numbers starting with [REDACTED]. The PID will ultimately comprise the site number and participant number. For example, the first participant screened (ie, enrolled) at site number 1 will have a PID of [REDACTED]. Once it is determined that the participant meets the eligibility criteria, he or she will be assigned to the applicable cohort during the screening visit.

7.3 Blinding

This is an open-label study. Participants, site personnel (eg, monitors and investigators), and Sponsor personnel will not be blinded to therapy.

7.4 Dosage Modification

Additional dose modification after the 7-day titration is not allowed.

7.5 Preparation/Handling/Storage/Accountability

The IP must be stored in a secure area according to local regulations. It is the responsibility of the investigator or the designee, where permitted, to ensure that the IP is only dispensed to study participants. The IP must be dispensed only from official study sites by authorized personnel according to local regulations.

The product storage manager should ensure that the study intervention is stored in accordance with the environmental conditions (temperature, light, and humidity) determined by BMS. If concerns regarding the quality or appearance of the study intervention arise, the study intervention should not be dispensed, and BMS should be contacted immediately.

Documentation of IP must be maintained that includes all processes required to ensure the drug is accurately administered. This includes documentation of drug storage, administration, and, as applicable, storage temperatures, etc.

- The investigator or designee must confirm that appropriate temperature conditions have been maintained during transit for all study intervention received and that any discrepancies are reported and resolved before use of the study intervention.
- The investigator, institution, or the head of the medical institution (where applicable) is responsible for study intervention accountability, reconciliation, and record maintenance (ie, receipt, reconciliation, and final disposition records).
- Further guidance and information for the final disposition of unused study interventions are provided in the Study Reference Manual.

7.6 Treatment Compliance

Study intervention compliance will be periodically (see [Table 2-1](#) and [Table 2-2](#)) monitored for drug accountability. Drug accountability should be reviewed by the site study staff at each visit to

confirm treatment compliance. Sites should discuss discrepancies with the participants at each on-treatment study visit.

When participants self-administer study intervention(s) at home, compliance with the study intervention will be assessed at each visit. Compliance will be assessed by counting returned capsules during site visits and will be documented in the source documents and relevant form. Deviation(s) from the prescribed dosage regimen should be recorded in the electronic case report form (eCRF).

A record of the quantity of study intervention dispensed to and taken by each participant must be maintained and reconciled with study intervention and compliance records. Intervention start and stop dates, including dates of intervention delays and/or dose reductions, will also be recorded in the eCRF.

7.7 Concomitant Therapy

7.7.1 Prohibited and/or Restricted Treatments

Prohibited and/or restricted medications taken prior to study intervention administration in the study are described below. Medications taken prior to study intervention administration must be recorded on the eCRF.

- Prior exposure to ozanimod is prohibited.
- Exposure to any investigational drug or placebo within 4 weeks of study intervention administration is prohibited.
- Prohibited concomitant medications are listed in Table 7.7-1.

Table 7.7-1: Summary of Prohibited Concomitant Medications

Immunomodulatory Drugs	
• eg, Thiopurines, methotrexate, cyclosporin, tacrolimus.• Prohibited, with a required washout period of at least 1 day.
Advanced Therapies for the Treatment of UC	
• Biologic agents and small molecules.• Prohibited with required washout periods prior to study initiation of at least 8 weeks or 5 elimination half lives, whichever is shorter.• Washout period may be waived with the demonstration of absent drug levels on a TDM assay.
Monoamine Oxidase Inhibitors	
• Prohibited during ozanimod treatment.• 14-day washout period prior to the first study intervention administration.
Live or Live-attenuated Vaccines	
• Prohibited during ozanimod treatment.• 30-day washout period prior to the first study intervention administration.• Avoid use for up to 3 months after discontinuation of the study intervention.

Table 7.7-1: Summary of Prohibited Concomitant Medications

Therapy for Current Active or Any Major Infections	
 Patients who require antibiotic treatment (oral or IV) for current active or any major infections are excluded.
Alemtuzumab	
 Prohibited during ozanimod treatment. Confirm B cell recovery prior to the first study intervention administration.
Beta Interferon	
 Prohibited during ozanimod treatment.
Glatiramer Acetate	
 Prohibited during ozanimod treatment.

Restricted concomitant medications and foods are listed in Table 7.7-2.

Table 7.7-2: Summary of Restricted Concomitant Medications and Foods

NSAIDs	
 May be used as clinically indicated during the study. Oral NSAIDs may be associated with GI toxicity, including mucosal injury. Consequently, their use is not recommended.
Inactivated or Subunit Vaccines	
 May be used as clinically indicated during the study. The effect of ozanimod treatment on responses to vaccination is not known.
Antiarrhythmic Drugs with Known Arrhythmogenic Properties	
 Ozanimod has not been studied in patients taking QT-prolonging drugs. Class Ia (eg, quinidine, procainamide) and Class III (eg, amiodarone, sotalol) antiarrhythmic drugs have been associated with cases of torsades de pointes in patients with bradycardia. Advice from a cardiologist should be sought prior to the initiation of treatment with ozanimod.
Combination Beta Blocker and a Calcium Channel Blocker	
 Co-administration of ozanimod with both a beta blocker and a calcium channel blocker has not been studied. However, there is potential for additive effects on HR. Advice from a cardiologist should be sought prior to the initiation of treatment with ozanimod.
Adrenergic and Serotonergic Drugs	
 Co-administration of ozanimod with drugs or over-the-counter medications that can increase norepinephrine or serotonin (eg, opioid drugs, SSRIs, SNRIs, tricyclic antidepressants, tyramine) will be per product label. Monitor participants for hypertension with concomitant use.
Foods Containing a Large Amount of Tyramine	
 Participants should be advised to avoid foods containing a large amount of tyramine during the treatment period. Aged, fermented, cured, smoked, and pickled foods containing large amounts of exogenous amines (eg, aged cheese, pickled herring) may cause the release of norepinephrine, resulting in an increase in blood pressure (tyramine reaction).
Strong CYP2C8 Inducers	
 Use of strong CYP2C8 inducers (eg, rifampicin) should be avoided.

Table 7.7-2: Summary of Restricted Concomitant Medications and Foods

	
 Co-administration of ozanimod with strong CYP2C8 inducers reduces the exposure of the major active metabolites of ozanimod, which may decrease the efficacy of ozanimod.
--	--

CYP2C8, cytochrome P4502C8; NSAID, non-steroidal anti-inflammatory drugs; SNRI, serotonin-norepinephrine reuptake inhibitor; SSRI, selective serotonin reuptake inhibitor.

Dose stabilization rules for permitted concomitant medications are listed in Table 7.7-3.

Table 7.7-3: Summary of Dose Stabilization Rules for Permitted Concomitant Medications

Oral and Rectal 5-ASAs	
 Oral and rectal 5-ASAs are permitted. Stable doses are encouraged after the first study intervention administration, particularly up to the assessment of the primary endpoint.
Rectal Corticosteroids	
 Rectal corticosteroids are permitted as clinically indicated. After assessment of the primary endpoint, rectal corticosteroids are only allowed for a maximum of 3 months per year (eg, rectal corticosteroids are permitted during induction, and one other course is permitted as indicated within Year 1; only one 3-month course is permitted per year thereafter).
Oral Prednisone	
 Cannot be on oral prednisone continuously for more than 28 days prior to Day 1. Oral prednisone \leq40 mg QD PO (or equivalent) is permitted at Day 1, if clinically indicated, and is permitted at that dose for no more than 14 days prior. Tapering schedule will be as follows: Reduce dose by 5 mg weekly until 20 mg is reached, then reduce by 2.5 mg weekly to 0 mg. Tapering can occur more rapidly at the investigator's discretion. Patient should be on prednisone continuously for no more than 12 weeks. One rescue course of prednisone (up to 40 mg QD PO with subsequent tapering, as described above) will be permitted per year, not including prednisone use in the first 12 weeks of the study. The maximum duration of each course is 12 weeks.
Oral Budesonide	
 Budesonide \leq9 mg QD PO is permitted at Day 1, if clinically indicated. Dose should be stable for 14 days prior to the first study intervention administration. One rescue course of budesonide will be permitted each year with a maximum course duration of 12 weeks and tapering at the investigator's discretion. The investigator may switch between prednisone and budesonide for the rescue treatment. The maximum duration of 12 weeks applies, irrespective of steroid switching.

7.7.2 Other Restrictions and Precautions

Participants are prohibited from joining another interventional clinical trial while they are participating in this study.

7.7.2.1 Treatment Failure Rules

Treatment failure rules will be applied to the primary analyses of all efficacy endpoints. Participants will be considered to have failed treatment if any of the following occur:

- Any protocol-prohibited change in medications, including:
 - Post-baseline initiation of or increase in total daily dose to a level higher than the 40 mg maximum permitted dose of corticosteroid to treat UC.
 - Prolonged course of systemic corticosteroids (ie, > 12 consecutive weeks) for treatment of UC.
 - Initiation of an immune-suppressing therapy, including 6-mercaptopurine, AZA, methotrexate, anti-TNF agents, anti-integrin, anti-IL-12/23 agents, or JAK inhibitors.
- A colectomy (partial or total) or an ostomy.
- Discontinuation of the study intervention due to lack of therapeutic effect before primary or secondary efficacy evaluations.

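### Rescue steroids permitted before the primary visit do not clearly count as treatment failure, so they can contribute to the single-arm response rate (clearest in Cohort 2); the 12-week steroid limit also lacks a stated counting day.

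*Combined protocol and SAP*

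**What the plan says.** Section 7.7.2.1 states that "Treatment failure rules will be applied to the primary analyses of all efficacy endpoints". Its medication limb is headed "Any protocol-prohibited change in medications, including", and two bullets under it concern steroids. The first covers post-baseline steroid "initiation of or increase in total daily dose to a level higher than the 40 mg maximum permitted dose of corticosteroid to treat UC". The second reads "Prolonged course of systemic corticosteroids (ie, > 12 consecutive weeks) for treatment of UC". Section 10.3 makes participants non-responders if they stop study drug or take prohibited concomitant medication before the primary visit.

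Corticosteroids are not in the prohibited list (Table 7.7-1). They are in Table 7.7-3 (section 7.7.1), which permits prednisone up to 40 mg at Day 1 with a taper: "Reduce dose by 5 mg weekly until 20 mg is reached, then reduce by 2.5 mg weekly to 0 mg". A faster taper is allowed at the investigator's discretion. One prednisone rescue course of up to 40 mg "will be permitted per year, not including prednisone use in the first 12 weeks of the study", and one budesonide rescue course is allowed each year. Each course may last at most 12 weeks. On duration, the table says "Patient should be on prednisone continuously for no more than 12 weeks", and on use before the study, "Cannot be on oral prednisone continuously for more than 28 days prior to Day 1".

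Clinical response (Table 10.4.3-1 and Appendix 6) is defined on the modified Mayo score alone. At a primary visit, the only steroid-free endpoint is corticosteroid-free remission in Cohort 2 at Week 26.

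**The concern.** The primary result in each cohort is a response rate with no comparator (section 10.1), so improvement helped by a permitted steroid course has nothing to offset it. Section 3.2.1 itself describes corticosteroids as effective at bringing about remission. The available text does not let a reader see how many responders had such a course. Section 10.4.2 summarises steroid use at screening and UC medication at baseline, section 10.4.3 names sensitivity analyses only for missing data, and the steroid-free endpoint at Week 26 concerns remission, not response.

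A second, smaller matter works in the other direction. If the 12-week limit is counted from before Day 1, someone who followed the printed taper could be scored as a non-responder.

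**Working it through.** **The plan's own figures.** Exact (Clopper-Pearson) 95% intervals reproduce those in section 10.2: 75/150 gives 41.74% to 58.26% (stated 41.7% to 58.3%), and 45/100 gives 35.03% to 55.27% (stated 35% to 55.3%).

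**Length of the printed taper from 40 mg** (Table 7.7-3, one week per step). 40, 35, 30, 25 is 4 weeks; 20, 17.5, 15, 12.5, 10, 7.5, 5, 2.5 is 8 weeks. The total is 12 weeks, or 84 days.

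**Cohort 2 timing** (Week 26 is Day 182 in Table 2-1). Take the earliest prednisone rescue as Day 85, after the first 12 weeks. A course that starts on day s has its last dose on day s + 83.
- s = 85: last dose Day 168. s = 98: Day 181. Both end before the visit.
- s = 99: last dose Day 182. From here on the course is still running at the visit.
- Dose on Day 182: 2.5 mg for s = 99 to 105, 10 mg for s = 126, 20 mg for s = 154, 40 mg for s = 176 to 181.
- Start days 85 to 181 number 97, and start days 99 to 181 number 83.

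**Cohort 1 timing.** A participant who enters on 40 mg and follows the printed taper takes the last dose on Day 84, the nominal Week 12 visit. New prednisone starts within the first 12 weeks are implied by the rescue wording, not stated. Budesonide rescue is not barred in that period.

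**Can response be met on symptoms alone?** Section 6.1 requires SF 1-3, RB 1-3 and ES 2-3, which gives 3 × 3 × 2 = 18 baseline profiles with totals from 4 to 9. Hold ES unchanged and set SF = RB = 0. The fall is SF + RB ≥ 2 points, the relative fall is at least 2/(2 + 3) = 40%, above the required 35%, and RB is 0. All 18 profiles can qualify with no endoscopic change. After Week 12, SF and RB are recorded for the 7 days before each visit (Table 2-1).

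**Size.** One participant is 1/150 = 0.67 points in Cohort 1 and 1/100 = 1.0 point in Cohort 2. The documents give no rate of steroid use, so the numbers rescored below are assumptions.

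| Responders rescored | Cohort 2, from 45/100 | Cohort 1, from 75/150 |
|---|---|---|
| 5 | 40.0% (30.3 to 50.3) | 46.7% (38.5 to 55.0) |
| 10 | 35.0% (25.7 to 45.2) | 43.3% (35.3 to 51.7) |
| 15 | 30.0% (21.2 to 40.0) | 40.0% (32.1 to 48.3) |

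Ten in Cohort 2 would span the 35% to 45% planning range in section 10.2.

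**The 12-week limit.** Counted from Day 1, the longest printed taper is exactly 12 weeks and does not exceed the limit. If prior days count, the totals in weeks are:

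| Day 1 dose | From Day 1 | +7 days | +14 days | +28 days |
|---|---|---|---|---|
| 40 mg | 12 | 13 | 14 | 16 |
| 35 mg | 11 | 12 | 13 | 15 |
| 30 mg | 10 | 11 | 12 | 14 |
| 25 mg | 9 | 10 | 11 | 13 |
| 20 mg | 8 | 9 | 10 | 12 |

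Where the total exceeds 12 weeks, the 85th consecutive day falls on Day 85 minus the prior days: Day 78, 71 or 57, all before Day 84.

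**The case against.** Counting permitted steroid users as responders is a coherent choice for a descriptive study in clinical practice with no hypothesis test. That stands, and it is why the primary rule need not change.

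The steroid bullet begins with post-baseline initiation and can be parsed as failing any new steroid start. On that reading a rescue course is scored as failure. The heading about prohibited changes favours the other reading but does not exclude this one. If it is the intended one, the section contradicts the rescue course in Table 7.7-3, so the wording needs reconciling either way.

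The protocol defers sensitivity and detailed analyses to a SAP that was not available, and the subsection between 10.4.4 and 10.4.6 is blacked out. A reader might infer that no steroid analysis is planned; the documents do not support that.

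A reader might also take 83 of 97 start days as a probability, or conclude that the response rate is inflated. Neither follows. The count is of calendar days on one dose and the slowest taper, not of participants. The 18-profile result is a property of the response definition, with or without steroids, and requires both symptom subscores to reach 0.

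Finally, one might infer that the printed taper breaches the failure rule. It does not if counting starts on Day 1. If earlier days count, it first exceeds Table 7.7-3's own 12-week cap, and the permitted faster taper can avoid both. What stands is the unstated counting day.

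**Conclusion.** The point holds as a gap in scoring and reporting, not as a demonstrated bias. On the reading favoured by the heading of section 7.7.2.1, a participant who needed a permitted rescue course, or is still on one at the visit, can count toward an uncontrolled response rate. This is clearest in Cohort 2. On the other reading, sections 7.7.1 and 7.7.2.1 contradict each other. The effect on the rate cannot be sized from the documents; only the per-participant step is known (1.0 point in Cohort 2, 0.67 in Cohort 1).

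The 12-week point is narrower. There is a conflict only if permitted days before Day 1 count and the printed taper is followed without shortening. Whether oral budesonide counts is also unstated: section 7.7.2.1 refers to corticosteroid and systemic corticosteroids, Appendix 6 to oral systemic steroid, and neither mentions budesonide.

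These conclusions assume one week per taper step, a first rescue day of Day 85, and nominal visit days.

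**What to change.** These changes concern scoring and reporting only; permitted treatment is untouched.

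1. Keep the primary analysis. For each cohort, prespecify a supplementary response rate that counts as non-responders those who, between Day 1 and the primary visit, started a new systemic corticosteroid or oral budesonide course for UC or rose above their Day 1 dose. Report how many are rescored. Report separately how many responders are still taking an oral steroid at the primary visit, so that Cohort 1 participants on the Day 1 taper are visible. If the SAP already contains this, cite it in the protocol.
2. Reconcile the steroid bullet in section 7.7.2.1 with the rescue course in Table 7.7-3 so that only one reading is possible.
3. Reconcile the 12-week limit in section 7.7.2.1 with Table 7.7-3 and state the day from which weeks are counted for scoring. State whether oral budesonide counts in the failure rule and in corticosteroid-free remission.

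The cost is some wording and one extra analysis, using medication data already scheduled for collection at each visit (Tables 2-1 and 2-2). The supplementary rate can only equal or fall below the primary rate, and it answers a different question, so it should be labelled supplementary.

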7.8 Continued Access to Study Intervention After the End of the Study

At the end of the study, BMS will not continue to provide BMS-supplied study interventions to participants or investigators unless BMS chooses to extend the study. The investigator should ensure that the participant receives the appropriate standard of care to treat the condition under study.

8 DISCONTINUATION CRITERIA

8.1 Discontinuation From Study Intervention

Participants MUST discontinue IP for any of the following reasons:

- Participant's or investigator's request to stop study intervention. Participants who request to discontinue study intervention will remain in the study and must continue to be followed for the protocol-specified follow-up procedures. The only exception to this is when a participant specifically withdraws consent for any further contact with him/her or persons previously authorized by the participant to provide this information.
- Any clinical AE, laboratory abnormality, intercurrent illness, or other appropriate reason(s), which, in the opinion of the investigator, indicates that continued administration of study intervention is not in the best interest of the participant.
- Termination of the study by BMS.
- Loss of ability to freely provide consent through imprisonment or involuntarily incarceration for treatment of either a psychiatric or physical (eg, infectious disease) illness. (Note: Under specific circumstances and only in countries where local regulations permit, a participant who has been imprisoned may be permitted to continue as a participant. Strict conditions apply, and BMS approval is required.)

- Pregnancy (refer to [Section 9.2.5](#)).
- Significant non-compliance with the protocol (eg, procedures, assessments, medications). The investigator should discuss such issues with the Medical Monitor.
- Participant meets one of the following criteria for laboratory abnormalities in 2 sequential laboratory measurements taken up to 14 days apart:
 - Hb < 7.0 g/dL or a decrease of >30% from baseline
 - Lymphocyte count < $0.2 \times 10^9/\text{L}$ ($< 200/\text{mm}^3$) – see [Section 9.2.6](#) for temporary discontinuation guidance.
- Participant meets any of the following criteria for liver-related laboratory abnormalities. If these abnormalities are identified, repeat testing should occur within 48 to 72 hours, and these results should be discussed with the BMS Medical Monitor or designee. Additional recommendations on the recognition and investigation of potential drug-induced liver injury (DILI) are given in [Section 9.2.7](#).
 - ALT or AST > $8 \times \text{ULN}$ on a single occasion.
 - ALT or AST > $5 \times \text{ULN}$ for more than 2 weeks.
 - ALT or AST > $3 \times \text{ULN}$ and total bilirubin > $2 \times \text{ULN}$ or international normalized ratio (INR) > 1.5.
 - ALT or AST > $3 \times \text{ULN}$ with the appearance of fatigue, nausea, vomiting, right upper quadrant pain or tenderness, fever, rash, and/or eosinophilia (> 5%).

Refer to the SOA for the data that will be collected at the time of treatment discontinuation and follow-up and for any further evaluations that can be completed.

All participants who discontinue study intervention should comply with the protocol-specified follow-up procedures, as outlined in [Section 2](#). The only exception to this requirement is when a participant withdraws consent for all study procedures, including post-treatment study follow-up, or loses the ability to consent freely (eg, is imprisoned or involuntarily incarcerated for the treatment of either a psychiatric or physical illness).

If study intervention is discontinued prior to the participant's completion of the study, the reason for the discontinuation must be documented in the participant's medical records, per local regulatory requirements in each region/country, as applicable, and entered on the appropriate eCRF page.

8.1.1 *Treatment Interruption*

Participants should be instructed that if they forget to take a dose, they can take it within 4 hours of the normal dosing time; otherwise, they should take their next dose at the regular time on the following day. If the participant vomits the dose, he/she should be instructed not to take another dose on the same day, but to take the next dose at the regular time on the following day. Participants will record whether they took the daily dose of medication in an electronic diary that will be reviewed periodically by the site staff and the site monitor.

If a dose is missed during the first 2 weeks of treatment, re-initiate treatment using dose escalation regimen. If a dose of study intervention is missed after the first 2 weeks of treatment, continue with the treatment as planned. If more than 7 consecutive days between Day 15 and Day 28 of treatment, or more than 14 consecutive days after Day 28 of treatment, re-initiate treatment using the dose escalation regimen. The Medical Monitor should be contacted to discuss completing the dose escalation schedule.

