- Malignancy: Participants should be carefully monitored for malignancies (including dermatologic malignancy). The investigator will complete dermatological examinations to monitor the potential development of new cutaneous malignancies during the study. Participants with any suspicious finding noted during the examination will be referred to an appropriately qualified dermatologist for evaluation and treatment, if warranted.
- Serious or opportunistic infection: Tuberculosis, serious bacterial infections, systemic fungal infections, viral infections, such as herpes infections (including herpes zoster and disseminated herpes simplex), and protozoan infections will be considered AEIs.
- Pulmonary effects: If a participant discontinues due to a respiratory AE, the investigator should ensure that the participant has had adequate evaluations, as clinically indicated by a pulmonologist (consider pulmonary function tests, chest X-ray, or high-resolution computed tomography, based on findings of the other examinations), at the time of the AE.
- Hepatic effects: If participants have elevations in liver function tests (LFTs; ALT or/and AST) $\geq 3 \times$ ULN, a retest should be performed as soon as possible but no later than 14 days after the original test. Upon confirmation of the abnormality, retests should be performed weekly until the elevated LFT decreases to below $3 \times$ ULN. At any time, if any of the following occur and there are no apparent alternative causes for the finding, the study intervention must be permanently discontinued:
 - ALT or AST $> 8 \times$ ULN or
 - ALT or AST $> 5 \times$ ULN with confirmation within 2 weeks or
 - ALT or AST $> 3 \times$ ULN and (total bilirubin $> 2 \times$ ULN or INR > 1.5) or
 - ALT or AST $> 3 \times$ ULN with the appearance of fatigue, nausea, vomiting, right upper quadrant pain or tenderness, fever, rash, and/or eosinophilia ($> 5\%$).
- The investigator should establish causality.
- After discontinuation due to elevation of ALT or AST $> 5 \times$ ULN or concurrent elevations of ALT or AST $> 3 \times$ ULN and bilirubin $> 2 \times$ ULN, further liver function evaluations should be performed (for example, coagulation panel and alkaline phosphatase) in consultation with the Medical Monitor.

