9.2.6 Laboratory Test Result Abnormalities

The following laboratory test result abnormalities should be captured on the nonserious AE eCRF page or SAE eCRF, as appropriate. Paper forms are only intended as a back-up option when the electronic system is not functioning.

- Reductions in absolute lymphocyte count (ALC) levels for participants in this study are an expected primary PD effect. If $ALC < 200 \text{ cells}/\mu\text{L}$ results are observed during the study, the investigator will be notified and asked to repeat the laboratory tests within 14 days. If the repeat ALC is confirmed below the $200 \text{ cells}/\mu\text{L}$ limit, the investigator will temporarily discontinue study intervention. Laboratory testing will be repeated weekly until the ALC is $> 500 \text{ cells}/\mu\text{L}$. For participants who have a confirmed ALC below the $200 \text{ cells}/\mu\text{L}$ limit and decide to permanently discontinue study intervention, central laboratory testing will continue every 14 days (± 3 days) after the end of treatment visit until it is above the lower limit of normal or until the ALC is considered to have stabilized and/or reached a level that is not clinically significant. Reductions in ALC, in general, need not be reported as AEs unless there are clinical consequences. The decision to report decreased ALC as an AE is at the investigator's discretion.
- Any laboratory test result that is clinically significant or meets the definition of an SAE.

- Any laboratory test result abnormality that required the participant to have study intervention discontinued or interrupted.
- Any laboratory test result abnormality that required the participant to receive specific corrective therapy.

It is expected that, wherever possible, the clinical term would be used by the reporting investigator rather than the laboratory term (eg, anemia vs low Hb value).

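### Sections 8.1 and 9.2.1.1 set mandatory liver stopping criteria that differ above 5 × ULN, on alternative causes and on retest timing, and nothing says how they combine

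*Combined protocol and SAP*

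**What the plan says.** Section 8.1 heads its list "Participants MUST discontinue IP for any of the following reasons". Its liver bullet is met by any one of four findings: ALT or AST > 8 × ULN once; > 5 × ULN "for more than 2 weeks"; > 3 × ULN together with a bilirubin or INR limit; or > 3 × ULN with listed symptoms or eosinophilia. The bullet asks for repeat testing within 48 to 72 hours and discussion with the Medical Monitor or designee. For further guidance it refers only to Section 9.2.7.

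The hepatic paragraph of Section 9.2.1.1 lists nearly the same four findings. Its second criterion is ALT or AST above 5 × "ULN with confirmation within 2 weeks". The whole list is conditional: it applies where "there are no apparent alternative causes for the finding, the study intervention must be permanently discontinued". For ALT or AST at or above 3 × ULN, this section wants a retest as soon as possible and at the latest 14 days after the original test, then weekly retests once the abnormality is confirmed.

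Section 9.2.1.1 does not mention Section 8.1. Section 9.2.7 defines potential drug-induced liver injury for reporting and contains no stopping rule. Table 3.3.1-1 handles liver injury by reference to the product label, which is not among the documents.

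**The concern.** Two current, mandatory lists address the same laboratory findings in nearly the same words but set different conditions. An investigator who looks up the rule in one section will not always reach the same decision as a colleague who looks it up in the other. Nothing says which list governs, or that both apply together.

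The stake is consistent handling of a named adverse event of interest in a multicenter, open-label study with two years of dosing, no Data Monitoring Committee (Section 5.1.1) and no protocol waivers (Section 9). A site relying on one section could keep a participant on drug when the other section requires a stop.

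**Working it through.** This is a comparison of text; the plan states no figure to reproduce.

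**Side by side**

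| Item | Section 8.1 | Section 9.2.1.1 |
|---|---|---|
| > 8 × ULN | one occasion | no qualifier |
| > 5 × ULN | lasting more than 2 weeks | confirmed within 2 weeks |
| Alternative cause | no condition | list applies only if none is apparent |
| Retest | 48 to 72 hours | as soon as possible, at most 14 days |
| Permanence | not stated | permanent |
| Bilirubin/INR | no brackets | the two limits bracketed together |

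**Reading the 5 × criterion.** Let Day 0 be the first value above 5 × ULN. More than 2 weeks means more than 14 days, so Section 8.1 cannot be met before Day 15. Within 2 weeks means by Day 14, so Section 9.2.1.1 is met, if at all, on or before Day 14. One is a duration rule and the other a confirmation rule.

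**Illustrative cases.** The values are assumptions chosen to exercise the rules. ALT/AST is raised in isolation, with no bilirubin, INR or symptom criterion met.

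| Course | Other cause apparent? | 8.1 liver criteria | 9.2.1.1 |
|---|---|---|---|
| 6, 5.5, 4 × ULN on Days 0, 7, 14 | no | not met | met, Day 7 |
| Same | yes | not met | not met |
| 9 × ULN once | no | met, Day 0 | met, Day 0 |
| 9 × ULN once | yes | met, Day 0 | not met |
| 6 × ULN for 21 days, confirmed on Day 7 | no | met after Day 14 | met, Day 7 |
| Same | yes | met after Day 14 | not met |

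Row 1 meets only Section 9.2.1.1. Rows 4 and 6 meet only Section 8.1. Neither list is therefore uniformly the stricter one.

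**If either list is enough to stop.** With another cause apparent, Section 8.1 would still require a stop for > 8 × ULN, for > 3 × ULN with bilirubin or INR, for > 3 × ULN with symptoms, and for > 5 × ULN lasting more than 2 weeks. The alternative-cause condition would then decide whether to stop only for a confirmed value above 5 × ULN that does not last beyond 2 weeks. A condition written to govern a whole list would have little left to do, so this reading cannot simply be assumed to be intended.

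**Retest.** A repeat at 48 to 72 hours also falls inside 14 days, so both instructions can be followed. A site using only Section 9.2.1.1 could retest on Day 14 and be outside the Section 8.1 window.

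**The case against.** The strongest reply is that the lists do not contradict each other. Each gives conditions sufficient to require a stop; neither says that drug continues when its own conditions are unmet. Stopping whenever either list is met would comply with both. Section 9.2.1.1 also contains a mandatory stop, for confirmed new-onset macular edema, that Section 8.1 does not list by name, which favors reading the sections as additive. All of this stands. A reader might infer that no investigator could obey both sections, and that would be wrong. What remains is that the protocol never states the additive reading, and that this reading nearly empties the alternative-cause condition.

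That condition might instead govern only whether a stop is permanent. The second mismatch would then disappear, but the difference above 5 × ULN would stay.

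A reader might also infer a head-on conflict over permanence. The documents do not support that: Section 8.1 is silent, not contrary. The silence is not decisive either way. Treatment interruption has its own Section 8.1.1, but the lymphocyte criterion under the same Section 8.1 heading refers elsewhere "for temporary discontinuation guidance", and Section 9.2.6 says "the investigator will temporarily discontinue study intervention" and treats the permanent case separately. This is a minor point.

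The missing brackets in Section 8.1 might suggest that INR > 1.5 triggers a stop alone. In practice this matters little: INR is not in the routine laboratory list of Table 9.5.4-1, and the Year 2 schedule allows it, at the physician's discretion, when ALT or AST exceeds 3 × ULN.

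Safeguards exist. Section 8.1 lets the investigator stop for any laboratory abnormality on clinical judgment, Medical Monitor discussion is expected, and Section 9 sends immediate safety concerns to the Sponsor. These make silent reliance on one list less likely, but they do not say which criteria those discussions should apply.

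**Conclusion.** The mismatch is real in three respects: duration against confirmation above 5 × ULN, the alternative-cause condition, and retest timing. The lists can trigger differently in both directions. This is a gap in how two co-mandatory lists fit together, with possible inconsistency in safety management across sites. It is not an impossibility of compliance.

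The conclusion rests on the text and on reading 2 weeks as 14 days. It does not depend on the illustrative enzyme values, which only show that divergence can occur. A reader might want to turn the 5 × difference into a fixed delay in stopping. The documents do not support one figure, because it would depend on an assumed enzyme course and test schedule and on reading each section in isolation.

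Nor can an effect on results be sized. Under Section 10.3, stopping before Week 12 (Cohort 1) or Week 26 (Cohort 2) makes a participant a non-responder, so each responder reclassified would move the rate by 1/150 = 0.67 points or 1/100 = 1.0 point. The documents give no count of such participants. Any statistical effect is secondary to the safety-conduct issue.

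**What to change.** Reconcile the two passages into one set of liver stopping and retest criteria, state it once, and have the other section refer to it. The text should settle:

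- the duration or confirmation condition above 5 × ULN;
- the role of an alternative cause, including whether it bears on stopping or only on permanence;
- the retest interval;
- whether discontinuation is permanent;
- how the bilirubin and INR limits are grouped.

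The sponsor's clinical team decides the content; this review takes no view on which criterion is right. If both lists are meant to apply together, the protocol should say so expressly.

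The cost is a protocol amendment with IRB/IEC approval, as Appendix 2 requires, and notification of sites. The reconciliation itself needs no change to sample size or analysis method.
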